2 SYNOPSIS

Protocol title	A Phase 2 Multicenter, Open-Label, Uncontrolled Study to Evaluate the Safety, Tolerability, Efficacy, Pharmacokinetics, and Pharmacodynamics of RA101495 in Subjects with Paroxysmal Nocturnal Hemoglobinuria
Protocol number	RA101495-01.201
Phase of clinical development	Phase 2
Investigational medicinal product	RA101495 administered by daily subcutaneous injection
Study Population	Adults with paroxysmal nocturnal hemoglobinuria (PNH)
Investigative Sites	Approximately 10 centers are planned in one or more of the following locations: Australia, Canada, Germany, New Zealand and United Kingdom
Planned number of subjects	Up to 20 subjects will be enrolled in the study in two cohorts: 
 • Cohort A (Eculizumab Naïve): approximately 8-12 subjects • Cohort B (Eculizumab Switch): approximately 6-8 subjects
Study objectives	
 • To assess the safety and tolerability of RA101495 in subjects with PNH • To assess preliminary efficacy of RA101495 in subjects with PNH • To assess the pharmacokinetics (PK) and pharmacodynamics (PD) of RA101495 in subjects with PNH
Study design	
Study RA101495-01.201 is a multicenter, open-label, uncontrolled study to evaluate the safety, tolerability, efficacy, pharmacokinetics and pharmacodynamics of RA101495 in subjects with PNH.
 
The study will enroll two separate cohorts based on prior eculizumab treatment history.
 
 • Cohort A (Naïve) will include subjects who have not received eculizumab for treatment of PNH • Cohort B (Switch) will include subjects who have received treatment with eculizumab for at least 6 months prior to Screening. 
The planned enrollment is approximately 8-12 subjects in Cohort A and approximately 6-8 subjects in Cohort B, for a total of up to 20 subjects.
 
Cohort A will commence enrollment prior to Cohort B. Cohort B will not be opened until safety and efficacy data from at least 2 subjects completing the Week 2 Visit in Cohort A have been reviewed by the Sponsor and Study Investigators, and evidence of hemolysis suppression is demonstrated.
 
The study includes an 8-week screening period and a 12-week Treatment Period. During the Treatment Period, subjects will return to the clinic weekly for the first 4 weeks followed by visits every 2 weeks to evaluate safety, tolerability, efficacy, PK and PD. Additional assessments will include immunogenicity, Quality of Life (QOL) questionnaires, biomarker samples, and optional pharmacogenomics. Safety assessments include physical exam, vital signs, electrocardiogram (ECG), clinical laboratory tests, and adverse

	
events (AEs).
 
The risk of Neisseria meningitidis infection will be closely monitored during the study. During the screening period, prior to study entry, all subjects must have a documented negative result for Neisseria meningitidis colonization via a throat swab. All Cohort A (Naïve) subjects who have not been previously vaccinated against Neisseria meningitidis prior to study entry must be vaccinated and must receive ciprofloxacin for 14 days starting with the first dose of RA101495 at the Day 1 Visit. A booster vaccination should also be administered as clinically indicated according to the local standard of care. All Cohort B (Switch) subjects must have documentation of prior Neisseria meningitidis vaccination (and booster if appropriate) prior to study entry.
 
For Cohort A (Naïve) subjects, the Day 1 Visit may be scheduled at any time after Screening and confirmation of eligibility. For Cohort B (Switch) subjects, the Day 1 Visit should be scheduled to coincide with the next scheduled dose of eculizumab (i.e. 14 ± 2 days after from the last eculizumab dose). Eculizumab should NOT be administered at the Day 1 Visit or at anytime thereafter during the study
 
During the Treatment Period, to mitigate the risk of infection, subjects will be counseled and reminded of early signs and symptoms of Neisseria meningitidis infection. A patient safety card detailing the signs and symptoms of infection with instructions to seek immediate medical attention will be provided to each subject. The card will also describe the subject’s participation in the study and the risks of infection associated with inhibition of the terminal complement system. The patient safety card must be carried with the patient at all times while on treatment.
 
At the conclusion of the Treatment Period subjects who complete the study and are demonstrating benefit will have the option to enroll in an extension study to continue receiving treatment with RA101495. Alternatively, they may opt to receive standard-of-care treatment off study, after consultation with their treating physician. If the subject withdraws early from the RA101495-01.201 study for any reason, he/she will not be eligible for the extension study.
 
All subjects will receive a loading dose of 0.3 mg/kg to be administered subcutaneously (SC) at the Day 1 visit. Following in-clinic education and training, all subjects will self-administer daily SC doses of 0.1 mg/kg of RA101495 for 12 weeks. Except for Day 1, on study clinic days, the dose should be administered after the PK and PD collection has been completed.
 
From the Week 2 Visit onwards, if a subject has not achieved an adequate response (defined as a lactate dehydrogenase [LDH] <1.5 x ULN), and following evaluation of safety and tolerability data by the investigator and the medical monitor, the dose should be escalated to 0.3 mg/kg daily. The dose may also be escalated to 0.3 mg/kg daily at any time in the event of an overt breakthrough hemolysis episode (e.g. hemoglobinuria).


Duration of study participation
	
The total duration of study participation for all subjects will include a Screening Period of up to 8 weeks and a 12-week Treatment Period for a total of up to 20 weeks.

Study population
	
To be eligible for this study, subjects must meet ALL of the following

	
inclusion criteria:
 
1. Male or female ≥ 18 years2. Completed informed consent procedures, including signing and dating the informed consent form (ICF)3. Diagnosis of PNH by flow cytometry4. Cohort A (Naïve) subjects must not have received treatment with eculizumab prior to or during the Screening Period and must have a lactate dehydrogenase (LDH) level ≥ 2 times the upper limit of normal (xULN) during Screening5. Cohort B (Switch) subjects must have received treatment with eculizumab for at least 6 months prior to Screening6. Female subjects of child-bearing potential must have a negative pregnancy test at Screening and within 24-hours prior to the first dose of RA1014957. Sexually-active female subjects of child-bearing potential (i.e. women who are not post-menopausal or who have not had a bilateral oophorectomy, hysterectomy, or tubal ligation) and all male subjects (who have not been surgically sterilized by vasectomy) must agree to use effective contraception during the study. Effective contraception is defined as:
○ Hormonal contraception (e.g. oral contraceptive, transdermal contraceptive, contraceptive implant, or injectable hormonal contraceptive) for at least 3 months prior to study drug administration, throughout the study, and for 4 weeks after the last dose of study drug.○ Double-barrier birth control (e.g. male condom, female condom, diaphragm sponge, or cervical cap together with spermicidal foam/gel/film/suppository) starting at the Screening visit, throughout the study, and for 4 weeks after the last dose of study drug.○ Intrauterine contraception/device starting at the Screening visit, throughout the study, and for 4 weeks after the last dose of study drug.○ Total abstinence from sexual intercourse for at least one complete menstrual cycle prior to the Screening visit, throughout the study, and for 4 weeks after the last dose of study drug○ Maintenance of a monogamous relationship with a male partner who has been surgically sterilized by vasectomy. 
Subjects who meet ANY of the following exclusion criteria must be excluded from the study:
 
1. Platelet count $< 30,000/\mu\text{L}$ or absolute neutrophil count (ANC) < 500 cells/μL at Screening2. Calculated glomerular filtration rate of < 30 mL/min/1.73m^2 based on modification of diet in renal disease (MDRD) equation at Screening3. Elevation of liver function tests: alanine aminotransferase (ALT) $> 2\text{xULN}$ or Direct Bilirubin and Alkaline Phosphatase both $> 2\text{xULN}$4. Elevation of amylase or lipase $> 2\text{xULN}$
--	---

	
 5. History of meningococcal disease 6. Current systemic infection or suspicion of active bacterial infection 7. Pregnant, planning to become pregnant, or nursing female subjects 8. Recent surgery requiring general anesthesia within the 2 weeks prior to Screening, or expected to have surgery requiring general anesthesia during the 12-week Treatment Period 9. Active malignancy requiring surgery, chemotherapy, or radiation within the prior 12-months (subjects with a history of malignancy who have undergone curative resection or otherwise not requiring treatment for at least 12-months prior to Screening with no detectable recurrence are allowed) 10. History of any significant medical or psychiatric disorder that in the opinion of the investigator would make the subject unsuitable for participation in the study 11. Treatment with any investigational medicinal product or investigational device within the 30 days prior to Screening or participation in another concurrent clinical trial involving a therapeutic intervention (participation in observational studies and/or registry studies is permitted) 12. Unable or unwilling to comply with the requirements of the study

Endpoints and Assessments
	
Safety and Tolerability Safety assessments will include evaluation of AEs and SAEs (including major adverse vascular event (MAVE criteria), clinical laboratory tests, ECGs, vital signs, and physical examinations. Safety evaluations will also include a determination of anti-drug antibodies (ADA).
 
Primary Efficacy:
 
 • The primary evaluation period is from Week 6 to Week 12. The primary efficacy endpoint is the change-from-baseline in serum LDH levels during this period, defined as the mean LDH values of Weeks 6, 8, 10, and 12 minus the baseline value of LDH. 
Secondary Efficacy:
 
 • Changes from baseline in LDH, total bilirubin, total hemoglobin, free hemoglobin, haptoglobin, reticulocytes, and hemoglobinuria, at each of the scheduled post-baseline assessment time-points. 
Pharmacokinetic:
 
 • Plasma concentrations of RA101495 and its major metabolites • Maximum plasma concentration (C_{max}) • Time corresponding to C_{max} (t_{max}) • Area under the drug concentration-time curves (AUC_{0-t}) • Plasma concentrations of eculizumab (Cohort B only) 
Pharmacodynamic:
 
 • Changes from baseline CH_{50} • Changes from baseline in sheep RBC (sRBC) lysis for classical complement pathway • Changes from baseline in Wieslab enzyme-linked immunosorbent assay

	
(ELISA) for alternative complement pathway
 
 • Changes from baseline in C5 levels 
Exploratory:
 
 • Changes from baseline in quality of life (QOL) questionnaires (e.g. EORTC QLQ-C30, FACIT-Fatigue, and EQ-5D) • Treatment satisfaction questionnaire • Mechanistic biomarkers (e.g. complement function, complement proteins, biomarkers of inflammation, biomarkers for thrombosis, biomarkers of liver function) • Pharmacogenomic analyses (optional)

Statistical considerations
	
Study Populations: The following study populations are defined:
 
 • Safety Population: All subjects who receive at least 1 dose of RA101495 • Efficacy Evaluable Population: All subjects in the Safety Population who complete the 12-week Treatment Period • Per Protocol Population: All subjects in the Safety Population who complete the 12-week Treatment Period and have no major protocol deviations • PK Population: All subjects in the Safety Population who have at least 1 plasma sample obtained for PK assessment • PD Population: All subjects in the Safety Population who have at least 1 plasma sample obtained for PD assessment 
General Considerations: Data will be summarized within each cohort separately. Where appropriate, data may be summarized for the overall study.
 
A disposition of all consented subjects will be provided and will include a breakdown of subjects who consented, were treated, discontinued treatment, were lost to follow-up, or withdrew consent.
 
Continuous variables will be summarized with the mean, standard deviation (SD) median, and range. Categorical variables will be summarized using counts and proportions.
 
Safety: Adverse events will be coded using the Medical Dictionary for Regulatory Activities (MedDRA) (version 18.0 or higher). Incidence rates for treatment-emergent AEs (TEAEs) by maximum severity and SAEs will be summarized. These summaries will be provided regardless of causality and for events that are considered related to treatment with RA101495.
 
Quantitative laboratory endpoints will be summarized by cohort and time point and also by pooling cohorts.
 
Descriptive statistics for ECG parameters (i.e. heart rate [HR], PR interval, RR interval, QRS interval, QT interval, QTcB interval, and QTcF interval) at each assessment time point will be presented.
 
Descriptive statistics for vital signs (heart rate, body temperature, and blood pressure) will be presented.
 
The complete set of physical examination findings will be provided in listings. Clinically significant physical examination abnormalities will be included and summarized as AEs if appropriate.

	
Efficacy: Efficacy endpoints will be summarized by cohort. No formal statistical comparisons between cohorts will be performed. Tests to assess change-from-baseline will be applied to endpoints as appropriate.
 
For Cohort A (Naïve), the primary efficacy endpoint will be tested against a null hypothesis of a median change-from-baseline of 0 by a 2-sided Wilcoxon signed-rank test.
 
For Cohort B (Switch) an inferential test of the change-from-baseline primary efficacy endpoint will not be performed. Summary statistics for the primary endpoint will be provided including the mean, median, standard deviation, and standard error.
 
Pharmacokinetics: Drug exposure in the different cohorts will be evaluated using PK parameters derived from non-compartmental methods. All calculations for the final analysis will be based on actual sampling times. Individual PK parameters will be presented in listings and summarized by cohort and overall using descriptive statistics.
 
Pharmacodynamics: Pharmacodynamics will be summarized by cohort. No formal statistical comparisons between cohorts will be performed. Tests to assess change-from-baseline will be applied to endpoints as appropriate.
 
Determination of Sample Size: For Cohort A (Naïve) a sample size of 8 subjects yields approximately 95% power to reject the null hypothesis that the median LDH change-from-baseline is 0 for the primary efficacy endpoint. This assumes a mean decrease in LDH from 2200 U/L at baseline to 327 U/L during the primary evaluation period (Weeks 6-12) with corresponding standard deviations of 1034 U/L and 443 U/L, respectively, and a within-subject correlation estimate of 0. This yields a change-from-baseline mean of 1873 U/L and standard deviation of 1125 U/L. The power is based on a 2-sided Wilcoxon signed-rank test, at the 0.05 significance level.
 
For Cohort B (Switch) a sample size of 6 subjects will yield a standard error of approximately 114 U/L for an LDH mean change-from-baseline estimate. This assumes a standard deviation of 443 U/L for the baseline and post-baseline endpoints and a within-subject correlation estimate of 0.8, which yields change-from-baseline standard deviation of 280 U/L.
 
Interim Analysis: During this open-label study, the Sponsor will review safety and efficacy data as it becomes available during the Treatment Period. Following completion of the 12-week Treatment Period, data will be cleaned and locked at the individual subject level, and will be available for final analysis by the Sponsor on a rolling basis. Completion and final data lock of Cohort A may occur before, and independent, of Cohort B, or vice versa.

--	---

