6.3 CLINICAL TRIAL EXPERIENCE WITH RA101495

Clinical trial experience with RA101495 to date includes a single Phase 1 study (RA10145-1001) in healthy volunteers. The study RA101495-1001 was a randomized, double-blind, placebo-controlled, single-ascending-dose (SAD) and multiple-dose (MD) study designed to evaluate the safety, pharmacokinetics (PK), and pharmacodynamics (PD) of RA101495.

The first part of the study (SAD) evaluated a single dose of RA101495 versus placebo at 4 dose levels (0.05, 0.1, 0.2 and 0.4 mg/kg) in separate cohorts. The SAD enrolled 22 subjects; 14 received RA101495 (0.05 mg/kg in two subjects; 0.1, 0.2 and 0.4 mg/kg in four subjects each) and eight subjects received placebo, two per each dose level.

The second part of the study (MD) evaluated 7 daily doses of RA101495 versus placebo at a single dose level (0.2 mg/kg). The MD enrolled six subjects; four received RA101495 and two received placebo.

RA101495 when administered as a single dose and with 7-day repeat dosing displayed consistent and predictable PK that tightly correlated with the PD effect (inhibition of hemolysis and suppression of complement activity).

The plasma concentrations of RA101495 following single-dose SC administration (SAD) showed dose-dependent increases across all dose levels examined (0.05, 0.1, 0.2, and 0.4 mg/kg) (Figure 3). The mean C_{max} ranged from 1010 to 5873 ng/mL across doses. The mean AUC_{0-24} ranged from 21,440 to 112,300 ng* h/mL across doses. The mean half-life ($t_{1/2}$) was consistent across dose levels and ranged from 155.6 to 185.4 hours.

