In the multiple dose (MD) portion of the study, the day 1 mean C_{max} and AUC_{tau} were 2533 ng/mL and 50,010 ng*h/mL respectively, which were consistent with results from the 0.2 mg/kg single-dose cohort over the same post-dose period. Following daily sc administration for 7 days, the C_{max} and AUC_{tau} increased by approximately 2.9 and 3.0-fold respectively (Figure 4). Day 7 time to maximum plasma concentration (median T_{max} = 3.0 hours), total body clearance (mean CL/F = 1.3 mL/h/kg), elimination rate constant (K_{el} = 0.0043h⁻¹) and half-life ($t_{1/2}$ = 161.9 h) were all similar to single dose administration indicating that the absorption and elimination of RA101495 does not change significantly with repeat daily sc administration. The apparent volume of RA101495 distribution (V_z/F) showed some increase with administration of multiple doses of RA101495 (0.2 mg/kg SAD mean V_z/F = 71.4 mL/kg; 0.2 mg/kg MD mean day 7 V_z/F = 311.6 mL/kg). However, the day 7 V_z/F for RA101495 was still less than total body water suggesting that RA101495 does not distribute into the extravascular space upon repeat SC administration.

Figure 3 Mean (SD) Plasma RA101495 Concentrations Over Time by Dose Group Following Single-Dose SC Administration in Healthy Volunteers (Study RA101495-1001)

[figure not shown]
[figure not shown]

Figure 4 Mean (SD) Plasma RA101495 Concentrations Over Time by Dose Group Following Multiple-Dose SC Administration of 0.2 mg/kg for 7 Days in Healthy Volunteers (Study RA101495-1001)

RA101495 demonstrated strong pharmacodynamic effects on terminal complement. RA101495 administered as a single dose achieved rapid dose-dependent inhibition of *ex-vivo* hemolysis as measured by a sheep red blood cell (sRBC) lysis assay (Figure 5). The maximum PD effect was apparent approximately 3 hours after a single dose. The maximal percent inhibition of hemolysis compared to baseline reached $\geq 90\%$ for the 0.1, 0.2, and 0.4 mg/kg single-dose cohorts and 60% for the lowest dose (0.05 mg/kg) cohort. Mean hemolysis levels remained below baseline for up to 2 days in the 0.05 mg/kg cohort, up to 4 days in the 0.1 mg/kg cohort, and for up to 7 days in the 0.2 and 0.4 mg/kg cohorts.

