RA10495 administered for 7-days achieved inhibition of hemolysis that was rapid and sustained at $\geq 95\%$ across the dosing period in all subjects, (Figure 6). The mean percent inhibition of hemolysis compared to baseline reached $>95\%$ beginning at the first time point, 3 hours after dosing on Day 1, and continued throughout 7 days of dosing; all individual subjects showed $\geq 90\%$ inhibition of hemolysis at all time points. At 24 hours after the last dose, inhibition of hemolysis was observed to be $\geq 97\%$ in all subjects. Eight days after the last dose of RA10495, the mean inhibition of hemolysis remained $\geq 56\%$. Two subjects had inhibition of hemolysis $>70\%$ through 8 days after the last day of dosing. Hemolysis returned to pre-dose levels in all subjects within two weeks following the last dose.

Figure 5 Mean (SD) Red Blood Cell Lysis Over Time by Dose Group Following Single-Dose SC Administration in Healthy Volunteers (Study RA101495-1001)

[figure not shown]
[figure not shown]

Figure 6 Mean (SD) Red Blood Cell Lysis Over Time by Dose Group in the Multiple-Dose Cohort Once Daily for 7-Days in Healthy Volunteers in (Study RA101495-1001)

Note: Figure on the right is a duplicate of the figure on the left with an expanded y-axis.

Safety: Across all the SAD cohorts, 7 of the 14 of the subjects treated with RA101495, had adverse events (AEs), which occurred more frequently in the highest dose cohort (0.4 mg/kg). All subjects in the MD (0.2 mg/kg) had at least 1 AE. All AEs resolved. In all cohorts of the SAD and MD, there were no AEs that led to study drug discontinuation. No serious AEs (SAE) or deaths occurred during the study.

In the SAD the most common AEs regardless of causality in subjects who received single-doses of RA101495 were injection site erythema (3 subjects, cohort 4), upper respiratory tract infection (URI) (1 subject, cohort 1; 2 subjects, cohort 4), and headache (2 subjects, cohort 4). Other AEs that occurred in 1 subject each were bronchitis (cohort 1); catheter site phlebitis (cohort 3); fatigue (cohort 4); and back pain (cohort 4). AEs in subjects who received placebo were diarrhea, myalgia, headache, and rash, all in 1 subject each.

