6.4 DEVELOPMENT RATIONALE

RA101495 is being developed to treat patients with PNH. Based on PK and PD data generated to date, RA101495 has the potential to provide several advantages over the only currently approved therapy for PNH, eculizumab.

Daily administration of RA101495 is expected to result in near complete and sustained suppression of C5 for improved control of hemolysis. Continuous inhibition of hemolysis is important in the prevention of breakthrough hemolysis. Eculizumab at the approved dose of 900 mg biweekly has been associated with breakthrough hemolysis in some patients requiring dose increases beyond the approved dose described in the current product label [Hill 2005]. Breakthrough hemolysis with eculizumab treatment typically occurs towards the end the biweekly infusion cycle and has been shown to be associated with sub-therapeutic eculizumab levels at those time points [Nakayama, 2016; Brodsky, 2014]. Daily dosing with RA101495 is designed to ensure that C5 is continuously inhibited and is therefore expected to eliminate end-of-cycle breakthrough episodes.

As a self-administered SC product, RA101495 has the potential to improve treatment satisfaction and improve dosing convenience for patients with PNH, and may enable a reduction in the cost of providing care. The current standard-of-care requires health professionals to administer eculizumab via a biweekly intravenous (IV) infusion. Published studies of patient preferences for SC versus IV therapy show a clear preference for SC administration, and SC administration has been shown to increase compliance, patient satisfaction and QOL, as well as reduce treatment costs, drug requirements, and the complications of intravenous access [Stoner, 2015; Besarab, 2002]. Phase 2 studies of RA101495 will include quantitative instruments for evaluating QOL.

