6.5 DOSE JUSTIFICATION FOR STUDY

6.5.1 RATIONALE FOR STARTING DOSE (0.1 MG/KG)

The 0.1 mg/kg/day dose was selected to satisfy the following criteria:

- Predicted steady state drug levels for the nominal as well as the maximum dose (based on weight bracketing) are below the no observed adverse effect level (NOAEL) values for C_{max} and AUC_{0-24} observed in toxicology studies (Table 2)

[figure not shown]
- Predicted steady state C_{max} and AUC_{0-24} are not expected to exceed the values observed during the Phase 1 RA101495-1001 MD study in healthy volunteers (Table 2)
- Inhibition of hemolysis is expected to be maintained at $\geq 90\%$ at all times (following a loading dose of 0.3 mg/kg; see Section 6.5.2). This prediction is supported by overlaying the expected RA101495 plasma concentrations at steady state, with the PK/PD relationship obtained from Phase 1 studies in healthy volunteers (Figure 7). Adequate and sustained control of hemolysis is a key component of both efficacy and safety in PNH. In this disease, even a modest transient decrease in complement blockade can lead to immediate “breakthrough” intravascular hemolysis and recrudescence of severe PNH symptoms. This consideration is particularly important with respect to the potential for missed doses.

Table 2 Experimental and Predicted PK Values for RA101495 in Humans

Pharmacokinetic Parameter	Statistic	RA101495 (2 mg/kg) NOAEL NHP	RA101495 (0.2 mg/kg) QDx7; Day 7 Human (SD)	RA101495 (0.1 mg/kg) Steady State Prediction in Human	
				Nominal (Minimal) 0.1 mg/kg QD	Maximum dose* 0.14 mg/kg QD
C_{max} ($\mu\text{g/mL}$)	Mean	33.8	7.29 (0.66)	6.57	7.12
AUC_{0-24} ($\text{h}\cdot\mu\text{g/mL}$)	Mean	573	151.3 (12)	141.5	152.8

*Indicates the potential maximum dose received by patients due to weight bracketed dosing

Figure 7 Predicted PK and PD Effects Resulting From Weight-Bracketed Dosing of RA101495 (0.1mg/kg daily)

[figure not shown]

Note: Predicted plasma concentration range (blue lines) resulting from weight-bracketed dosing of RA101495 at 0.1mg/kg daily and expected PD effect (% hemolysis).

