For Cohort A (Naïve) subjects, the Day 1 Visit may be scheduled at any time after Screening and confirmation of eligibility.

For Cohort B (Switch) subjects, the Day 1 Visit should be scheduled to coincide with the next scheduled dose of eculizumab (i.e. 14 ±2 days after from the last eculizumab dose). Eculizumab should NOT be administered at the Day 1 Visit or at anytime thereafter during the study.

During the Treatment Period to mitigate the risk of infection, subjects will be counseled and reminded of early signs and symptoms of *Neisseria meningitidis* infection. A patient safety card detailing the signs and symptoms of infection with instructions to seek immediate medical attention will be provided to each subject. The card will also describe the subject's participation in the study and the risks of infection associated with inhibition of the terminal complement system. The patient safety card must be carried with the patient at all times while on treatment.

At the conclusion of the Treatment Period subjects who complete the study and are demonstrating benefit will have the option to enroll in an open-label extension study to continue receiving treatment with RA101495 or they may receive standard-of-care treatment off study, after consultation with their treating physician. If the subject withdraws early from the study for any reason, he/she will not be eligible for the extension study.

All subjects will receive a loading dose of 0.3 mg/kg to be administered SC at the Day 1 visit. Following in-clinic education and training, all subjects will self-inject daily SC doses of 0.1mg/kg of study drug every 24 hours at approximately the same time each day for the subsequent 12 weeks. On study clinic days, the dose should be administered after the PK and PD collection has been completed.

From the Week 2 Visit onwards, if a subject has not achieved an adequate response (defined as an LDH <1.5 x ULN), and following evaluation of safety and tolerability data by the investigator and the medical monitor, the dose should be escalated to 0.3 mg/kg daily. The dose may also be escalated to 0.3 mg/kg daily at any time in the event of an overt breakthrough hemolysis episode (e.g. hemoglobinuria).

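### The duty to carry the infection safety card ends with treatment, but the protocol's Phase 1 data show complement inhibition persisting for about one to two weeks after the last dose

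*Protocol*

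**What the plan says.** The rule on the card appears in the Synopsis (Study design), Section 8.1 and Section 12.1.3.5, in the same words each time: "The patient safety card must be carried with the patient at all times while on treatment". Those sections give the card's purpose as telling subjects the signs of meningococcal infection, directing them to urgent care, and describing the infection risk of terminal complement inhibition. Counselling on early signs is likewise tied to the Treatment Period.

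The procedures for early discontinuation (8.4.1), withdrawal (8.4.2) and end of study (8.6) do not mention the card. Table 1 schedules no visit after Day 84.

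Section 6.3 describes how the drug effect wears off:

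- Repeated dosing, 0.2 mg/kg daily for 7 days: "Eight days after the last dose of RA10495, the mean inhibition of hemolysis remained" at least 56%. Then: "Hemolysis returned to pre-dose levels in all subjects within two weeks following the last dose".
- Single dose: mean hemolysis stayed below baseline for up to 2 days at 0.05 mg/kg, "up to 4 days in the 0.1 mg/kg cohort, and for up to 7 days in the 0.2 and 0.4 mg/kg cohorts".

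On who leaves the drug, Section 8.1 says: "If the subject withdraws early from the study for any reason, he/she will not be eligible for the extension study". Under Section 8.2.2, completers may decline the extension and go to standard of care.

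**The concern.** The protocol justifies the card by complement inhibition but ends the duty at the last dose, and its own data show that inhibition does not end there. A subject who stops, does not enter the extension and does not start eculizumab at once spends one to two weeks partly inhibited with no instruction to carry the card. In that period a prompt to seek care for fever or other early signs still has a purpose. What is at stake is patient safety; no estimate or test depends on it.

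**Working it through.** **1. Does any text extend the duty?** No. The three statements of the rule agree. Sections 8.4.1, 8.4.2 and 8.6 are silent, and the SAP does not deal with the card.

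**2. How long does the effect last after repeated dosing?** The source is Section 6.3: "The MD enrolled six subjects; four received RA101495 and two received placebo". Inhibition was measured by an ex vivo assay.

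| Time after last dose | Inhibition of hemolysis |
|---|---|
| 24 hours | at least 97% in all subjects |
| 8 days | mean at least 56%; two subjects above 70% |
| within 2 weeks | back to pre-dose levels in all subjects |

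**3. Is this consistent with the stated half-life?** The elimination rate constant of 0.0043 per hour gives ln 2 / 0.0043 = 161.2 h, against the stated 161.9 h. With first-order decline at 161.9 h, the drug remaining is:

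- Day 8: 2^(−192/161.9) = 0.44
- Day 14: 2^(−336/161.9) = 0.24

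Across the single-dose half-life range of 155.6 to 185.4 h, these become 0.42 to 0.49 and 0.22 to 0.29. A residual effect at day 8 is what one would expect.

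**4. Does the offset carry over to this trial's doses?**

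- *Loading dose alone (0.3 mg/kg):* the single doses on either side, 0.2 and 0.4 mg/kg, both gave up to 7 days.
- *0.1 mg/kg daily:* Section 6.5.1 says predicted steady-state Cmax and AUC "are not expected to exceed the values observed during the Phase 1 RA101495-1001 MD study in healthy volunteers". From Table 2, Cmax is 6.57/7.29 = 0.90 to 7.12/7.29 = 0.98 of the Phase 1 day 7 value, and AUC is 141.5/151.3 = 0.94 to 152.8/151.3 = 1.01. A similar offset is a fair expectation.
- *0.3 mg/kg daily:* the documents give no offset data. The period could be longer and cannot be estimated reliably.

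**5. Would four weeks be long enough at 0.3 mg/kg daily?** This tests the proposed window; it does not estimate how long inhibition lasts. Assume log-linear decline at 161.9 h and the same concentration–effect relation as in the volunteers. Four weeks is 336 h beyond the two-week Phase 1 offset, or 336/161.9 = 2.08 half-lives. It therefore covers a starting exposure up to 2^2.08 = 4.2 times Phase 1 day 7. Dose-proportional scaling from 0.1 mg/kg gives:

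| Dose | Cmax ratio | AUC ratio |
|---|---|---|
| 0.3 mg/kg | 3 × 6.57/7.29 = 2.7 | 3 × 141.5/151.3 = 2.8 |
| 0.42 mg/kg (top of Table 3) | 4.2 × 6.57/7.29 = 3.8 | 4.2 × 141.5/151.3 = 3.9 |

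All are below 4.2. With the longest reported half-life, the window covers 2^(336/185.4) = 3.5-fold. That is enough for 0.3 mg/kg but slightly short of the top bracket under proportional scaling.

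Two features of the documents suggest the check is cautious:

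- Exposure rises less than in proportion to dose. Table 2 predicts about 8% more Cmax (7.12/6.57) and AUC (152.8/141.5) for a 40% higher dose.
- Single-dose effect durations of 2, 4, 7 and 7 days mean that successive doublings of dose added about 2, 3 and 0 days. The check assumes 161.9/24 = 6.75 days per doubling of exposure.

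**The case against.** The strongest reply is that the practical gap is small and partly out of sight. The card's text is not in the documents and the consent pages were removed, so either may already give post-dose advice. The card is not among the items to be returned, so subjects keep it, and they have been counselled throughout treatment. Vaccination is given or documented before dosing (11.2.5.1), SAEs are collected to 30 days after the last dose (12.3.1.2), and early stoppers have an End-of-Study Visit (8.4.1). Subjects who go to eculizumab, described in Section 6.4 as the only approved therapy, are managed on another C5 inhibitor. The step from ex vivo inhibition to meningococcal risk is inferred, and the repeat-dose data come from four treated volunteers. Inhibition of 56% is well below the 90% that the protocol targets for efficacy. The four-week window is borrowed from contraception, and proportional scaling overstates exposure at 0.3 mg/kg. For a subject who withdraws consent, a carrying duty is largely advisory.

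Most of this stands, and it is why the point is minor. It does not remove the mismatch. SAE collection records harm after it happens and prompts no one to seek care. The protocol requires the card in addition to vaccination during treatment, so it does not treat vaccination as sufficient. The less-than-proportional exposure makes the four-week check more cautious. The unseen card text could make the protocol change a matter of consistency only, but the protocol's rule would still be the shorter one.

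**Conclusion.** The concern holds, as a minor patient-safety gap. The stated duty lapses while the inhibition that motivates the card continues: about one week after the loading dose alone, and at most two weeks after repeated dosing at exposures like those of Phase 1. For 0.3 mg/kg daily the period is unknown and may be longer. Those affected are an unknown minority of at most 20 subjects, chiefly those who stop and do not start eculizumab at once.

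The conclusion assumes that the volunteers' offset applies to subjects with PNH after up to 12 weeks of dosing, that residual inhibition carries some infection risk (the protocol's own reason for the card), and that the card does not already state a longer period. Confidence is medium. No endpoint, sample size or analysis is affected.

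**What to change.** In the Synopsis, Section 8.1 and Section 12.1.3.5, extend the duty to the treatment period plus 4 weeks after the last dose, and bring the card text into line if it differs. Two weeks is the minimum the Phase 1 data support and leaves no margin for 0.3 mg/kg daily. Four weeks gives that margin and matches the post-dose window already used for contraception in Section 9.1. Add a reminder to the End-of-Study Visit list in Section 8.4.1. Completers need no separate item, because the Week 12 visit falls within the Treatment Period, where counselling already applies.

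The cost is one phrase in three places, one line in 8.4.1 and possibly a reprinted card, with IEC/IRB approval under Section 14.3. No visit, sample or staff time is added.
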